12.2 Tabular Overview

PROCEDURE	TIME								
	Pre-operative	Randomization	Prior to induction of anesthesia	After induction of anesthesia	During surgery	End of surgery	Admission to ICU / IMC	6 hours after end of surgery	12 hours after end of surgery / ICU/IMC discharge (which occurs latest)
Inclusion / exclusion criteria	x								
Written informed consent	x								
Pregnancy test (woman)	x								
History, demographics, Apfel-Score	x								
pre-operative medication	x								
Randomization		x							
Surgery related data					x	x			
Time on ventilator				x	x	x	x	x	x
Ventilator settings				x	x	x	x	x	x
Set of catheters and final positioning of patient			x	x					
Infusion of the investigational test or reference products			continuously ^h						
Hemodynamics			x ^a	continuously ^e					
Drug monitoring and tolerance			continuously						
Drainage blood losses and estimated blood loss					x	x			
Set of urinary catheter			x						
Recording of							continuously		

TIME	Pre-operative	Randomization	Prior to induction of anesthesia	After induction of anesthesia	During surgery	End of surgery	Admission to ICU / IMC	6 hours after end of surgery	12 hours after end of surgery / ICU/IMC discharge (which occurs latest)
PROCEDURE									
secondary bleeding									
Laboratory (blood and / or urine sampling)			x ^a	x ^b	x ^b	x ^b	x	x	x ^g
Blood gas analysis			x	x ^f	x ^f	x ^f	x	x	x ^g
Coagulation			x				x	x	x ^g
ROTEM			x				x	x	x ^g
Platelet aggregation (only site Frankfurt / Main)			x				x	x	x ^g
Renal function			x				x		x ^g
(Serious) adverse events / reactions			continuously						
Concomitant medication incl. blood products			continuously						
Diuresis						x ^c			x ^d
Length of ICU / IMC stay									x ⁱ
Study termination									x ^d

a baseline

b Hb, aPTT, fibrinogen and PC serve as trigger for blood product-administration; blood gas analysis intraoperatively every 15 min including recovery room every hour

c cumulated diuresis from start of anesthesia until end of surgery

d cumulated diuresis from end of surgery until 12 hours after end of surgery or ICU/IMC discharge, which occurs latest

e intraoperative every 15 min; CVP minus PEEP and MAP serve as trigger for IP-administration

f intraoperative every 15 min, recovery room hourly

g 12 hours after end of surgery

h until 12 hours after end of surgery

i discharge from ICU / IMC

12.3 Assessment of Compliance

not applicable

12.4 Precautionary Measures

The following measures are listed in the respective SmPCs:

Gelafundin ISO 40 mg/ml / Gelafundin® 4%:

Gelatine solutions should be administered with caution to patients with a history of allergic diseases, e.g. asthma.

Gelatine preparations for volume replacement may rarely cause anaphylactoid reactions of varying degrees of severity. In order to detect the occurrence of an anaphylactoid reaction as early as possible, the first 20 – 30 ml should be infused slowly and under careful observation of the patient. Details of symptoms of anaphylactoid reactions and emergency measures, see section 11.4.

Attention must also be paid to the dilution of plasma proteins (e.g. albumin and coagulation factors), which must be adequately substituted if necessary.

Gelatine solutions should only be administered with caution to:

- elderly patients,
- patients at risk of circulatory overload e.g. patients with congestive heart failure, right or left ventricular insufficiency, hypertension, pulmonary oedema or renal insufficiency with oligo- or anuria,
- patients suffering from coagulation disorders, chronic liver disease, lung edema, intracranial hemorrhage.

In such cases gelatine solutions should only be given under careful monitoring of the patient's hemodynamic situation.

There is no sufficient experience with the use of gelatine solutions in children. Therefore, gelatine solutions should be used in children only after careful benefit-risk assessment, and with careful monitoring.

In states of dehydration the fluid deficit must be corrected first. Electrolytes should be substituted as required.

Checks of serum electrolyte concentrations and water balance are necessary, in particular in patients with coagulation disorders, chronic liver disease, hypernatremia, hypokalemia, dehydration, or impairment of renal function.

Special attention should be paid to the appearance of symptoms of hypocalcemia (e.g. signs of tetany, paresthesia); then specific corrective measures should be taken.

During compensation of severe blood losses by infusions of large amounts of gelatine solutions, the hematocrit must be monitored under any circumstances. The hematocrit should not decrease below the critical values of 25% in general and 30% in ICU patients.

Likewise in those situations the dilution effect on coagulation factors should be observed, especially in patients with existing disorders of hemostasis.

Because the product does not substitute lost plasma protein, it is advisable to check the plasma protein concentrations.

Gelatine solutions must not be infused through the same infusion line together with blood or blood products (packed cells, plasma and plasma fractions).

Laboratory blood tests (blood group or irregular antigens) are possible after gelatine infusions. Nevertheless it is recommended to draw blood samples before the infusion of gelatin solutions in order to avoid hampered interpretation of results.

Gelatine solutions may have an influence on the following clinical-chemical tests, leading to falsely high values:

- erythrocyte sedimentation rate,
- specific gravity of urine,
- unspecific protein assays, e.g. the biuret method.

Sterofundin ISO:

High volume infusion must only be used under specific monitoring in patients with mild to moderate cardiac or pulmonary failure.

Solutions containing sodium chloride should be administered with caution to patients with

- mild to moderate cardiac insufficiency, peripheral or pulmonary oedema or extracellular hyperhydration
- hypernatremia, hyperchloremia, hypertonic dehydration, hypertension, impaired renal function, present or imminent eclampsia, aldosteronism or other conditions or treatment (e.g. corticoids/steroids) associated with sodium retention

Solutions containing potassium salts should be administered with caution to patients with cardiac disease, conditions predisposing to hyperkalemia such as renal or adrenocortical insufficiency, acute dehydration, or extensive tissue destruction as occurs with severe burns.

Because of the presence of calcium

- Care should be taken to prevent extravasation during intravenous infusion.
- The solution should be given cautiously to patients with impaired renal function or diseases associated with elevated vitamin D concentrations such as sarcoidosis.

In case of concomitant blood transfusion, the solution must not be administered via the same infusion set.

Solutions containing metabolisable anions should be administered cautiously to patients with respiratory impairment. Monitoring of the serum electrolytes, fluid balance, and pH is necessary.

During long-term parenteral treatment, a convenient nutritive supply must be given to the patient.

Sodium Chloride 0.9%:

Sodium Chloride 0.9% should only be administered with caution in cases of

- hypokalemia
- hypernatremia
- hyperchloremia

- disorders where restriction of sodium intake is indicated, such as cardiac insufficiency, generalized oedema, pulmonary oedema, hypertension, eclampsia, severe renal insufficiency.

Clinical monitoring should include checks of the serum ionogram, the water balance, and the acid-base status.

High infusion rates should be avoided in cases of hypertonic dehydration because of possible increases of plasma osmolarity and plasma sodium concentration.

Each patient will be checked if he/she can be treated according to the protocol or not. Patients at risk should be treated with caution and be excluded if the IP regimen can not be applied as required.

13 STUDY AND TREATMENT DURATION

13.1 Duration per patient

Start of study: with randomization prior to anesthesia

Treatment period (administration of Investigational Products):

Start of administration: immediately before start of anesthesia

Duration of administration: intraoperatively and postoperatively
until 12 hours after end of surgery

End of study: 12 hours after end of surgery or discharge from ICU / IMC. In case that the discharge is the latest, only its date is to be documented.

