	
Clinical Outcome:
 
 ▪ Time on ventilator measurement: from intubation to extubation in hours; the need of reintubation as well as requirements of postoperative ventilatory support will be documented ▪ Length of stay in ICU / IMC (i.e. time of discharge from ICU / IMC) ▪ Secondary bleeding ▪ Concomitant medication/ therapy 
 ○ Start, end, drug / active substance, dose and unit, indication measurements: continuously during study period 
Other
 
 ▪ Demographic data 
 ○ Age, height, weight, sex, ASA-classification, concomitant disease, diagnosis, Apfel-Score (preoperative) ▪ Surgery related data 
 ○ Kind of intervention ○ Date of intervention ○ Duration of anesthesia ○ Duration of intervention

Patient Inclusion / Exclusion Criteria
	
Inclusion criteria:
 
 ▪ Male or female patients ≥ 18 years of age and ≤ 90 years of age. Women of child bearing potential must test negative on standard pregnancy test (urine dipsticks). ▪ Patients scheduled to undergo elective abdominal surgery (e.g. rectal resection, liver resection, open bowel resection, duodenopancreatectomy). ▪ Scheduled intraoperative volume requirement of at least 15 mL/kg body weight (Broca) gelatine solution ▪ Provision of voluntary consent to participate in the study, following a full explanation of the nature and purpose of the study, by signing the informed consent form approved by the Institutional Ethics Committee (IEC) prior to all evaluations. 
Exclusion criteria:
 
 ▪ Patients of ASA-class $> III$ ▪ Known hypersensitivity to gelatine or to any of the constituents of the solution ▪ Patients treated with other colloid solutions and / or blood products 24 hours prior to surgery ▪ Patients on hemodialysis ▪ Patients suffering from decompensated renal function (i.e. serum creatinine > 3.0 mg/dL) ▪ Patients suffering from 
 ○ Hypervolemia ○ Hyperhydration

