
Duration of Study per Patient
	
Start of study: randomization
 
Treatment period (infusion of Investigational Products):
 
immediately before induction of anesthesia until 12 hours after end of surgery
 
End of study: 12 hours after end of surgery or discharge from ICU / IMC. In case that the discharge is the latest, only its date is to be documented.

Study Schedule
	
Planned start: Q III 2011
 
Planned recruitment time: total sample size 1 year
 
Planned last patient out: Q III / Q IV 2012

Statistical Methods
	
The primary endpoints (BE and chloride) will be tested for difference between the two Gelofusine[®]-groups using a non-parametric statistical test (Mann-Whitney U-Test). This test is chosen with regard to small sample size and possible deviation from normal distribution.
 
All other parameters will be analysed exploratively. This analysis will also serve for testing of homogeneity of treatment groups at baseline.
 
All tests will be performed two-sided with an alpha-error $\alpha = 5\%$.

Randomization / Blinding
	
The patients will be randomised to either treatment in a 1:1 ratio.

	
Randomisation will be performed in permuted blocks.
 
Because of the bicentre study design the population will be stratified with regard to
 
▪ centre
Drug Safety Monitoring Board (DSMB)	not applicable (NA)

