10.2 Secondary Variables

10.2.1 Secondary Variables – Safety

Laboratory:

The analysis of blood and urine samples will be performed by the hospital laboratories according to the corresponding methods and guidelines (see Appendix 3). The reference ranges of these parameters are given in Appendix 4.

Blood samples for laboratory parameters will be taken, if not stated otherwise, at least:

- baseline i.e. prior to induction of anesthesia
- admission to ICU / IMC
- 6 hours after end of surgery
- 12 hours after end of surgery

Additional times will be listed in the context of the respective parameter.

The results of all blood analyses performed after blood sampling will be documented as follows:

- date and time of blood sampling [dd.mm.yyyy / hh:mm].

Arterial blood gas analyses

- pondus hydrogenii (pH); not temperature corrected.
- Base excess (BE) [mmol/L]
- Bicarbonate (HCO_3) [mmol/L]
- Lactate [mmol/L]
- Sodium (Na^+) [mmol/L]
- Potassium (K^+) [mmol/L]
- Calcium (Ca^{2+}) [mmol/L]
- Chloride (Cl^-) [mmol/L]
- Partial pressure of carbon dioxide (pCO_2) [mmHg]
- Partial pressure of oxygen (pO_2) [mmHg]
- Oxygen saturation (SaO_2) [%]
- Hemoglobin (Hb) [g/dL]
- Hematocrit (Hct) [%]

Hemoglobin acts as trigger for the administration of the blood products and will be monitored intraoperatively.

Additionally to the above mentioned measurements blood samples for arterial blood gas analysis will be taken intraoperatively every 15 min including recovery room every 60 minutes and additional measurements depending on the investigators decision.

Coagulation status

- Antithrombin III (AT III) [%]
- Fibrinogen [g/dL]
- Platelet count [μL]
- Activated partial thromboplastin time (aPTT) [s]

Fibrinogen, activated partial thromboplastin time (PTT), and platelet count act as trigger for the administration of the blood products and will be monitored intraoperatively.

These parameters will be recorded at baseline, at admission ICU /IMC, 6 hours and 12 hours after end of surgery.

- ROTEM (CT, MCF, LI 30)
- Platelet aggregation (TRAPtest, ASPItest, ADPtest) – only site Frankfurt am Main

These parameters will be recorded at baseline, at admission ICU /IMC, 6 hours and 12 hours after end of surgery.

Renal function

Blood samples:

- Serum creatinine (SCrea) [mg/g]
- Creatinine clearance [mL/min]
- Blood urea nitrogen (BUN) [mg/dL]
- Cystatin C [mg/L]

GFR and creatinine clearance will be calculated according to the Cockcroft-Gault Formula (see Chapter 14.1.1)

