10.3 Other variables**Demographic data**

- Age [years]
- Height [cm]
- Weight [kg]
- Sex
- ASA-classification
- Apfel-Score
- Concomitant disease

- Diagnosis

Measurements:

- pe-operatively / prior to anesthesia

Surgery related data

- Kind of intervention / precise classification of surgical intervention
- Date of intervention [dd.mm.yyyy]
- Start and end of anesthetics application [hh:mm]
- Start and end of intubation [hh:mm]
- Time of incision [hh:mm]
- Time of wound suture [hh:mm]

Measurements:

- during / after surgery

Clinical Outcome

- Time on ventilator
- Ventilator settings (i.e. frequency, minute volume, ventilation pressure)

Measurements:

- measured from intubation in hours or in case of setting changes
- reintubation will be documented
- requirements of postoperative ventilatory support will be documented

- Secondary bleeding

Measurements:

- after end of surgery until 12 hours after end of surgery

- Length of stay on ICU / IMC

Measurements:

- admission to ICU / IMC
- discharge from the ICU / IMC

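### For ICU/IMC discharges later than 12 hours after surgery the protocol asks for the date only, yet the synopsis ties length of stay to the time of discharge, leaving late stays uncertain by up to about 24 hours

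*Protocol*

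**What the plan says.** The synopsis lists the variable under clinical outcome as "Length of stay in ICU / IMC (i.e. time of discharge from ICU / IMC", so it points to a time. The end-of-study rule, given in the synopsis (duration of study per patient) and again in section 13.1, is narrower. The study ends 12 hours after surgery or at ICU/IMC discharge, and for the later case "In case that the discharge is the latest, only its date is to be documented".

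Two other places might have resolved this and do not:

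- Section 10.3 lists "Length of stay on ICU / IMC" with admission and discharge as the measurement points, but gives no unit and no date or time format.
- The schedule in section 12.2 has only the footnote "i discharge from ICU / IMC".

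Where the protocol wants a clock time it normally says so, as in section 10.2.1: "date and time of blood sampling [dd.mm.yyyy / hh:mm".

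The analysis status is clear. Beyond base excess and chloride, "All other parameters will be analysed exploratively".

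**The concern.** This is a data-collection rule. A statistical analysis plan can choose how to derive length of stay, but it cannot recover a clock time that was never written down. A site that follows section 13.1 to the letter leaves the hour of discharge blank for every patient who stays beyond the 12-hour point.

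Three things follow. Late stays are known only coarsely. If they are counted in calendar days, the count depends on the hour of admission as well as on the length of the stay, so patients can be put in the wrong order. And if earlier discharges are recorded to the minute, one variable carries two resolutions. Section 14.1 plans nonparametric tests for the non-primary variables, and those tests depend on ordering and ties.

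At stake is the precision of one listed clinical outcome.

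**Working it through.** The protocol states no figure for length of stay, so there is none to reproduce.

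**1. What a date-only record leaves open**

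Let a be the clock hour of ICU/IMC admission and s the true stay in hours. The difference in calendar dates is

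days = floor((a + s) / 24),

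with a discharge at exactly midnight counted to the new day. A value of 1 therefore covers

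24 − a ≤ s < 48 − a,

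which is 24 hours wide whatever the value of a. For a discharge later than 12 hours after surgery, the stay must also exceed 12 − g, where g is the gap in hours from end of surgery to ICU/IMC admission. The documents give neither a nor g; both are assumptions here.

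| Assumed admission | All stays counted as 1 day | Late discharges only, g = 0 | g = 1 h | g = 3 h |
|---|---|---|---|---|
| 12:00 | 12–36 h | 12–36 h | 12–36 h | 12–36 h |
| 16:00 | 8–32 h | 12–32 h | 11–32 h | 9–32 h |
| 18:00 | 6–30 h | 12–30 h | 11–30 h | 9–30 h |
| 20:00 | 4–28 h | 12–28 h | 11–28 h | 9–28 h |

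**2. Same stay, different count**

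- 30 h, admitted 16:00: floor((16 + 30) / 24) = floor(46 / 24) = 1.
- 30 h, admitted 18:00: floor((18 + 30) / 24) = floor(48 / 24) = 2.

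Order can also reverse. A 31 h stay from 16:00 gives floor(47 / 24) = 1, which is below the 2 given to the shorter 30 h stay from 18:00.

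**3. Illustration of the effect on a comparison**

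Assumptions, none of them from the protocol: admission uniform between 11:00 and 19:00; stays lognormal with log-SD 0.6; g = 1 h; clock hours kept for discharges up to 12 hours after surgery; late discharges counted in calendar days; two-sided 5% Mann-Whitney test. The 32 per arm is the planned size.

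- With a median of 20 h, about 75% of late discharges are counted as 1 day. Their true stays run from about 11.5 to 33 h (central 95%).
- Power by assumed medians:

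| Medians | Hours for all | Late discharges in calendar days |
|---|---|---|
| 20 vs 30 h | about 74% | about 65% |
| 40 vs 60 h | about 73% | about 70% |

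Repeat runs move these by a point or two. The loss shrinks with longer stays because a one-day grid is then fine enough to keep most of the ordering. The derivation matters too: if the missing discharge time is set to noon, power in the 20 versus 30 h case is about 58 to 60%.

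**The case against.** The strongest defence is context. The sentence stands under the end of the study, and it may only have meant that nothing except the discharge is collected after 12 hours. The synopsis wording on time of discharge carries no clock format and could mean simply the point of discharge. Whole days are a usable resolution for ICU stay, derivation rules commonly belong in the analysis plan, and the case report form is not shown.

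Part of this stands. The intent may well have been harmless, and counting calendar dates is only one possible derivation. But as written the rule limits the record to a date. Section 10.3 itself separates the two, with a date format for the day of the intervention and a clock format for incision and suture. The end-of-study reading is also not applied consistently: footnote d in section 12.2 asks for "cumulated diuresis from end of surgery until 12 hours after end of surgery or ICU/IMC discharge, which occurs latest", which is more than a discharge date.

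A reader might go further and infer any of the following. The documents support none of them.

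- **That most patients are affected.** No expected length of stay is given.
- **That stays from about 9 hours up become 1 day under this rule.** A 9-hour stay is a late discharge only if ICU/IMC admission follows the end of surgery by about 3 hours, and no such gap is stated.
- **That the test loses 12 or more percentage points of power.** Losses of that size arise if every stay is date-coded, although the rule covers late discharges only, or if discharge is imputed at noon. Both also assume short stays.

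**Conclusion.** The inconsistency is real: the synopsis definition points to the time of discharge, the rule in the synopsis and section 13.1 keeps only the date, and neither section 10.3 nor section 12.2 reconciles them. The firm consequence is that a late stay is uncertain by up to about 24 hours and that its calendar-day count depends on the hour of admission. That follows from clock arithmetic and needs no assumption about the patients.

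The size of the effect on a group comparison is not known. The illustration gives a loss of about 9 percentage points for medians of 20 versus 30 h and about 3 points for 40 versus 60 h. Both rest on assumed admission hours, stay distribution, transfer gap and derivation.

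The consequence is minor. Length of stay is exploratory, no power is claimed for it, and the sample size in section 14.5 rests on base excess and chloride. It is still worth correcting, because the lost hour cannot be restored at the analysis stage.

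**What to change.** - In section 13.1 and the matching synopsis row, require both date and time of ICU/IMC discharge when it falls after the 12-hour point.
- In section 10.3, give the format for ICU/IMC admission and discharge as dd.mm.yyyy / hh:mm.
- Derive length of stay in hours, as discharge date and time minus admission date and time, for all patients regardless of when they leave.
- If the sentence was meant only to end other data collection after 12 hours, say so, and reconcile it with footnote d on diuresis in section 12.2.

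The cost is one extra clock-time field. Section 10.4 already names the patient chart as the source for ICU/IMC stay. Sample size, alpha and the primary analysis do not change.

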13.2 Duration of whole study

Planned study start: Q III 2011

Planned recruitment time: 1 year

Planned last patient out: Q III / Q IV 2012

14 STATISTICS

14.1 Statistical methods

This section gives an overview of the statistics planned for the study. All programming of tables, figures, listings and statistical analyses will be performed using the statistical software packages as SPSS® or SAS®. The planned statistics will be performed in accordance with the principles outlined by the guideline ICH E9.

A Statistical Analysis Plan (SAP) will be finalized before close of database. It includes all protocol amendments. In case a protocol amendment is passed after finalization of the SAP an amendment to the SAP is to be composed.

All target criteria (primary and secondary variables) will first be examined by exploratory data analysis and descriptively evaluated (Wernecke 1995). In this setting, the evaluation of structural homogeneity of the treatment groups will be performed for

the purpose of quality assurance. The primary endpoint (difference in acid base change between balanced and non-balanced volume replacement with gelatine solutions) will be evaluated with a non-parametric statistical test (Mann-Whitney U-test, Hartung and Elpelt, 1993) taking into consideration small sample sizes and possible deviation from normal distribution. The stratification variable 'site' will be included in the primary analysis as covariates (in a nonparametric analysis of covariance cf. Bathke, Brunner 2003).

Secondary target variables will also be evaluated with nonparametric tests according to their scaling. Whereby, in case of a small random sample size or an unbalanced condition, exact tests will be used (Mehta, Patel, 1998).

The following parameters will be calculated by the given formula in the course of the statistical analysis:

- Anion gap [mmol/L] using
Anion gap = Sodium + Potassium – Bicarbonate – Chloride
- Strong ion deficit (SID) [mmol/L] using
Strong ion difference = Sodium + Potassium – Chloride – Lactate
- Creatinine clearance / GFR using Cockcroft-Gault-Formula
Creatinine clearance
= $((140 - \text{age}) \times \text{weight}) / (72 \times \text{Serum creatinine})$ for male patients and
Creatinine clearance
= $((140 - \text{age}) \times \text{weight}) / (72 \times \text{Serum creatinine}) \times 0.85$
for female patients
- Ratio of applied blood product volume and estimated blood volume of the patient
- Ratio of time on ventilation and time of intervention (i.e. from skin incision until skin suture)

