14.3 Level of significance and power

All tests will be conducted with an error of 1st kind $\alpha = 5\%$, two-sided.

Tests of secondary variables will be carried out in the area of exploratory data analysis. Therefore, corresponding p-values are to be regarded as exploratory ones and no adjustments for multiple testing will be made.

Sample size calculations are to be performed with a power of 80%.

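### Time on ventilator and its ratio to operation time both carry operation length, in opposite directions, and are imprecise measures of ventilation after surgery (minor; exploratory variable)

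*Protocol*

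**What the plan says.** The synopsis lists time on ventilator under clinical outcome, measured "from intubation to extubation in hours". Section 10.3 also starts the clock at intubation ("measured from intubation in hours or in case of setting changes"). Section 14.1 then lists, among the parameters to be calculated by a given formula, the "Ratio of time on ventilation and time of intervention (i.e. from skin incision until skin suture").

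No duration counted from the end of surgery is defined. Section 10.3 says that reintubation will be documented and that "requirements of postoperative ventilatory support will be documented". The same section records "Start and end of intubation [hh:mm"] and "Time of wound suture [hh:mm"], so the two clock times needed for a postoperative duration are collected.

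On status, section 10.3 places the variable under other variables, while section 5.2 and the synopsis group clinical outcome with the secondary ones. Either way it is tested exploratively: section 14.3 states that "corresponding p-values are to be regarded as exploratory ones and no adjustments for multiple testing will be made".

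**The concern.** A fluid regimen could plausibly affect how long a patient stays ventilated after surgery. It has no evident way to change the time from intubation to incision or the length of the operation. The total adds both of these to the postoperative part. The ratio looks like an adjustment for operation length but does not isolate the postoperative part: the time before incision and after suture is divided by operation length, so the same postoperative ventilation scores lower after a long operation than after a short one.

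Operation length can be expected to vary. Section 7.2 gives rectal, liver and open bowel resection and duodenopancreatectomy as examples, and section 7.5 stratifies by centre only. At stake is how a reported ventilator result can be read. A null result on either measure could say little about postoperative ventilation, and the two measures could point in different directions for the same patients.

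**Working it through.** **Plan's own figure.** The protocol gives no figure for ventilation or operation time. The only figure used from it is the group size in section 14.5: 28 per group for base excess, and 28/0.9 = 31.1, rounded up to 32 per group. This reproduces.

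**Algebra (no assumptions).** Let pre = intubation to incision, op = incision to suture, post = suture to extubation.

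- Total T = pre + op + post. It rises one for one with op.
- Ratio R = T/op = 1 + (pre + post)/op. For fixed pre + post it falls as op rises.

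**Worked patients (assumed hours, pre = 0.75).**

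| Patient | op | post | T | R |
|---|---|---|---|---|
| A | 2 | 0.5 | 3.25 | 3.25/2 = 1.625 |
| B | 6 | 1.5 | 8.25 | 8.25/6 = 1.375 |
| C | 6 | 0.25 | 7.00 | 7.00/6 = 1.167 |
| D | 2 | 3 | 5.75 | 5.75/2 = 2.875 |

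The ratio ranks B better than A, although B was ventilated 1.5/0.5 = 3 times as long after surgery. The total ranks D better than C, although D was ventilated 3/0.25 = 12 times as long. Counting from suture orders all four correctly.

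**When does operation length dominate?** Simulated patients with lognormal durations: median op 3 to 4 h (log-SD 0.25 to 0.4), median pre 0.75 h, post as shown (log-SD 0.6 at 0.25 h, 1.0 at 1 h and 3 h). Spearman correlations:

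| Median post | T with op | T with post | R with op | R with post |
|---|---|---|---|---|
| 0.25 h | 0.95 to 0.98 | 0.11 to 0.16 | -0.65 to -0.81 | 0.31 to 0.41 |
| 1 h | 0.63 to 0.75 | 0.55 to 0.69 | -0.39 to -0.56 | 0.77 to 0.86 |
| 3 h | 0.33 to 0.46 | 0.84 to 0.91 | -0.30 to -0.45 | 0.87 to 0.94 |

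Pairs of patients ranked in the wrong order at 0.25 h: 45 to 47% for the total and 36 to 39% for the ratio. At 3 h: 11 to 17% across both.

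**Precision of the group comparison.** Assumptions: 32 per arm, op mean 4 h (SD 1.5), pre 0.5 to 1.5 h, post lognormal with log-SD 0.8, Mann-Whitney test at two-sided 5%. Approximate power:

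| Post medians | Suture to extubation | Total | Ratio |
|---|---|---|---|
| 0.5 vs 1.0 h | 91% | 28% | 50% |
| 0.75 vs 1.25 h | 70% | 23% | 37% |
| 3 vs 5 h | 70% | 58% | 52% |
| 6 vs 10 h | 70% | 65% | 56% |

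Repeated runs, including one with a lognormal operation time, moved these figures by up to about 4 points. With no effect, the false-positive rate was 4 to 5% for all three measures.

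**The case against.** The strongest case on the other side has five parts.

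- **Dominance by operation length.** A reader might infer that both measures mostly record how long surgery lasted and that this swamps any effect. The document does not support that. It gives no durations, and when postoperative ventilation is long the postoperative part dominates both measures. At medians of 6 vs 10 h the total loses only about 5 points of power. This part stands.
- **Intent.** A reader might also infer that prolonged ventilation after surgery was the outcome really meant. No passage says so. The protocol defines intubation to extubation explicitly and documents postoperative support as a separate item. This part stands too.
- **Bias.** Allocation is randomised 1:1, so operation length is balanced in expectation, and the test keeps its level. Mis-ordering individual patients does not bias the group comparison. This stands: the cost is precision and interpretability only.
- **Consequence.** The variable is exploratory, and neither the sample size nor any success criterion uses it. This stands and limits the grade.
- **Place.** Section 14.1 calls itself an overview, and a further derivation could be added in the SAP, which is not at hand. This stands only in part. The ratio is not a detail left open, because the protocol prescribes its formula and denominator.

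None of this removes the algebra, and suture-to-extubation time had the highest power in every scenario tried.

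**Conclusion.** The point holds as a minor one. Both prescribed measures are influenced by operation length, in opposite directions, and this follows from the definitions alone. Both can rank a patient with longer postoperative ventilation as better. For an effect confined to the time after surgery, both are less precise than a measure counted from wound suture. The loss is large when extubation is early (about 70% power down to 23% and 37%) and moderate when ventilation is long (about 70% down to 58% and 52% at 3 vs 5 h).

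The sizes rest entirely on assumed durations and on assumed effects that act only after suture. They show a range and do not predict this trial. Nothing here touches the primary analysis or the validity of the trial's conclusions.

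**What to change.** In section 14.1, add one derived parameter: postoperative ventilation time = end of intubation minus time of wound suture, both already recorded under section 10.3. Use it as the between-group ventilator comparison instead of the ratio. Keep intubation-to-extubation time, and the ratio if wanted, as descriptive. Rank patients still ventilated at the end of observation as longest, which suits the nonparametric test. Set this before unblinding.

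Report reintubation separately as documented. Add its duration only if clock times are available: section 10.3 says that reintubation will be documented but lists no start and stop times for it, so the protocol does not show that this part can be derived.

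Cost: one extra derivation, and the ratio loses its role as a tested measure. The main derivation needs no new data, visits or patients.
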